13. Screening labs outside the normal range for parameters associated with potential risk for treatment under investigation. This will include but is not limited to:
 - a. Platelets $\leq 120 \times 10^9/L$ or $\geq 600 \times 10^9/L$
 - b. Absolute neutrophil count $\leq 1.5 \times 10^9/L$
 - c. Hemoglobin levels $\leq 11 \text{ g/dL}$ for females, or hemoglobin levels $\leq 12.5 \text{ g/dL}$ for males
14. Screening blood glucose levels of hemoglobin A1c $\geq 6.5\%$ (48 mmol/mol).
15. Abnormal liver function at Screening, defined as $\geq 2 \times$ ULN of any 3 or more of the following: serum alanine transaminase, serum aspartate transaminase, serum alkaline phosphatase, total bilirubin.
16. Abnormal renal function (estimated glomerular filtration rate $<60 \text{ mL/min}/1.73 \text{ m}^2$ using the MDRD equation).
17. At screening, any active or previous Hepatitis B or C infection, or known human immunodeficiency virus infection.
18. Vaccination with herpes zoster vaccine or any live virus vaccine within 6 weeks prior to Screening or during the study.
19. Positive TB test, or history of incompletely treated or untreated tuberculosis.

NOTE: In cases where performance of a QuantiFERON-TB Gold test is not possible, testing with a Tuberculin Skin Test (TST) may be an option after consultation with the Medical Monitor. If the TST is negative, patients can be randomized into the study, assuming they meet all other inclusion and none of the exclusion criteria. If results are

equivocal, or there is reason to believe the result is a false positive, a QuantiFERON-TB Gold must be performed before a subject is eligible for randomization.

20. Prolonged QT or heart-rate corrected QT (QTc) interval with Fridericia's correction (QTcF) > 450 msec for males or QTcF > 470 msec for females.
21. History of alcohol, medication, or illicit drug abuse within 1 year before the first dose of study drug.
22. Females who are nursing, pregnant, or planning to become pregnant while in the study, and for 30 days after last dose of study medication.
23. Participation in another investigational study within the greater of 4 weeks or 5 half-lives of an investigational medication prior to screening or during the study.

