8.2. Safety Criteria and Management for Stopping Doses

Patients who experience hematologic adverse events as described in [Table 3](#) or adverse events that may reflect an unfavorable risk-benefit profile may have their dose interrupted or be discontinued from the study at the discretion of the Investigator. The Medical Monitor should be consulted whenever possible prior to decisions for dose interruption or patient discontinuation from the study.

Patients who require a dose interruption lasting more than 21 consecutive days will be discontinued from the study.

Patients who are discontinued from the study should undergo an Early Termination Visit and subsequent Safety Follow-up Visit as appropriate per [Section 7.3.1 Patient Withdrawal Procedures](#), and associated adverse events followed as described in [See Section 10 Adverse Events](#).

Hematology and serum chemistry parameters will be assessed every 2 weeks for the first 8 weeks of the Treatment, and every 4 weeks thereafter for the remainder of the study. Prior to dose interruption, hematology parameters should be confirmed with repeat testing at an interval deemed appropriate by the Investigator (e.g., at the next protocol-defined visit or an Unscheduled Visit), except in severe cases where immediate interruption of dosing is necessary for the safety of the patient. **Blood draws confirming dose interruption criteria should occur prior to the first daily dose on the day of draw.**

Dose interruption requirements for hematologic abnormalities are provided below. However, less significant changes may warrant clinical intervention and the Investigator should use his/her best clinical judgment when considering a dose interruption whether for singular or aggregate hematology results above the limits provided in [Table 3](#), or for other clinical signs, symptoms, or considerations that suggest dose interruption is in the best interest of the patient.

Table 3: Selected Hematologic Thresholds for Dose Interruption

Neutrophil Count	Dose Adjustment
Less than $1 \times 10^9/L$	Interrupt dose until recovered to greater than $1.5 \times 10^9/L$ and resume dosing at previous dose
Female Hemoglobin Level	Dose Adjustment
Less than 10 g/dL	Interrupt dose until recovered to greater than 11.5 g/dL and resume dosing at previous dose
Male Hemoglobin Level	Dose Adjustment
Less than 11.5 g/dL	Interrupt dose until recovered to greater than 13 g/dL and resume dosing at previous dose
Platelet Count	Dose Adjustment

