Less than $75 \times 10^9/L$	Interrupt dose until recovered to greater than $75 \times 10^9/L$ and resume dosing at previous dose
Greater than $750 \times 10^9/L$	Interrupt dose until recovered to less than $600 \times 10^9/L$ and resume dosing at previous dose

Upon dose interruption, the parameters that triggered the interruption should be monitored at least weekly until either: 1) recovery above the threshold for dosing resumption is achieved, or 2) the allowable 21-day interruption has elapsed. In the case of severe neutropenia (neutrophil counts less than $0.5 \times 10^9/L$) patients should discontinue the study drug and receive instructions to seek medical help if they develop fever or signs of infection. Patients who discontinue the study due to lack of acceptable recovery of parameters within 21 consecutive day dose interruption period should continue to be monitored as appropriate through acceptable clinical resolution.

If the patient recovers above the threshold for interruption before the 21 consecutive day interruption period ends, they may remain in the study. Subsequent dose interruptions within a patient should be discussed with the Medical Monitor to determine continued participation in the study.

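### Protocol 8.2 gives opposite instructions for a patient who lies between the interruption and resumption thresholds when a 21-day dose interruption runs out

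*Protocol*

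**What the plan says.** Four statements in Protocol 8.2 bear on a patient whose dose has been interrupted for a blood count.

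- **Table 3** sets an interruption level and a resumption level for each parameter. The male hemoglobin row interrupts below 11.5 g/dL and then reads: "Interrupt dose until recovered to greater than 13 g/dL and resume dosing at previous dose".
- **The monitoring sentence** below the table has the triggering parameter checked at least weekly until one of two end points: "recovery above the threshold for dosing resumption is achieved, or 2) the allowable 21-day interruption has elapsed".
- **The stay-in-study sentence** uses the other level: "If the patient recovers above the threshold for interruption before the 21 consecutive day interruption period ends, they may remain in the study".
- **The 21-day rule** reads: "Patients who require a dose interruption lasting more than 21 consecutive days will be discontinued from the study". Section 7.3.1 repeats it for interruptions made to manage adverse events, with *should* in place of *will*.

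On whether interruption is compulsory, 8.2 first says that patients with the Table 3 events "may have their dose interrupted or be discontinued from the study at the discretion of the Investigator". It later introduces the same table with: "Dose interruption requirements for hematologic abnormalities are provided below".

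At entry, Exclusion 13c (Protocol 7.2, with the same cut-offs in the Synopsis) rules out hemoglobin of 11 g/dL or less in women and 12.5 g/dL or less in men.

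**The concern.** The stay-in-study sentence and Table 3 refer to different thresholds. For most rows there is a gap between them, and a patient in that gap as the 21 days end gets two incompatible instructions. About 10 sites have to apply these sentences to individual laboratory values, and two sites that both follow the protocol could reach opposite decisions on the same result.

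What is at stake is mainly patient management: who stays, who is off drug and for how long, and who is discontinued. There is a smaller consequence for the data. Withdrawn patients are not replaced (Protocol 7.3), and a patient taken out early contributes an early-termination or carried-forward SALT score where a patient kept in could contribute one observed at 24 weeks.

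**Working it through.** No sample-size or power figure is involved, so the check is a comparison of stated limits. All interruption and resumption levels are from Protocol Table 3, and the entry limits are from Protocol 7.2, Exclusion 13.

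**Step 1. Gap between the two Table 3 levels.** Gap width is the distance between the interruption limit and the resumption limit.

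| Parameter | Interrupt | Resume | Values in conflict at day 21 | Width |
|---|---|---|---|---|
| Neutrophils (x10^9/L) | below 1.0 | above 1.5 | above 1.0 to 1.5 | 1.5 - 1.0 = 0.5 |
| Hemoglobin, female (g/dL) | below 10 | above 11.5 | above 10 to 11.5 | 11.5 - 10 = 1.5 |
| Hemoglobin, male (g/dL) | below 11.5 | above 13 | above 11.5 to 13 | 13 - 11.5 = 1.5 |
| Platelets, low (x10^9/L) | below 75 | above 75 | none | 75 - 75 = 0 |
| Platelets, high (x10^9/L) | above 750 | below 600 | 600 to below 750 | 750 - 600 = 150 |

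In the last row recovery means a fall. The word *above* in both the monitoring sentence and the stay-in-study sentence does not fit it. The conflict there assumes that the sentences are read in the direction the table row gives.

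**Step 2. Follow one patient through the sentences.** Take a woman whose hemoglobin falls to 9.8 g/dL and is back to 11.3 g/dL by day 21.

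- 9.8 is below 10, so Table 3 interrupts her dose.
- 11.3 is above 10, so the stay-in-study sentence lets her remain.
- 11.3 is not above 11.5, so Table 3 does not let her resume.
- Her interruption therefore passes 21 days, and the 21-day rule discontinues her.

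The second and fourth results cannot both be followed.

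**Step 3. Entry limits against resumption levels.** The shortfall is the resumption limit minus the entry limit, where positive.

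- Female hemoglobin: 11.5 - 11 = 0.5. Women above 11 and up to 11.5 g/dL pass the listed cut-off but are not above the resumption level.
- Male hemoglobin: 13 - 12.5 = 0.5. The same applies to men above 12.5 and up to 13 g/dL.
- Neutrophils: 1.5 - 1.5 = 0, so no shortfall.
- Platelets: entry requires above 120 and below 600. That is stricter than the low-platelet resumption level (75) and equal to the high one (600), so no shortfall.

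If the woman in Step 2 had entered at 11.3 g/dL, she would have regained her own entry value and still could not resume under Table 3.

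**The case against.** The strongest reply is that only one sentence is out of line. Table 3, the monitoring sentence and the 21-day rule agree with each other. The stay-in-study sentence is permissive and does not say that dosing restarts, so *remain* could mean remain off drug. The first part is right, and it narrows the fault. The second does not remove it: the 21-day rule discontinues a patient who stays off drug beyond that limit, and that is the patient the sentence says may remain.

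The Medical Monitor is to be consulted where possible before interruption or discontinuation, and repeat interruptions are to be discussed with the Medical Monitor. That makes divergent handling less likely, but it is no substitute for a written rule. It supports saying that sites *may* differ, not that they will.

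The wording about high platelets is a slip that few sites would misread, because the table row states the direction.

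A reader might infer that the entry limits contradict Table 3. The documents do not support that. Entry and restart limits answer different questions, nothing says they must match, and a higher level after an on-treatment fall may be intended. Nor can one say that enrolled patients start below the resumption level, since the documents hold no enrolled hemoglobin values. Exclusion 13 also opens more broadly than its cut-offs, with "Screening labs outside the normal range for parameters associated with potential risk for treatment under investigation", and lists those cut-offs as examples. Some of these patients could be excluded on that ground, but no normal range is given. The mismatch is therefore something to confirm, and for hemoglobin only.

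On discretion against requirement, the text can be read as a compulsory floor plus judgment for lesser changes. The first sentence is then loosely worded, and a clarification is enough.

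**Conclusion.** Protocol 8.2 is inconsistent as written. For neutrophils, hemoglobin in both sexes and high platelets, a patient within the gaps in Step 1 at day 21 may remain under one sentence and must be discontinued under another. Low platelets are not affected. Two secondary points need only the sponsor's confirmation: that the hemoglobin entry cut-offs are meant to lie 0.5 g/dL below the resumption levels, and whether Table 3 interruption is mandatory.

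It would be tempting to add that each such discontinuation removes Week 24 data and erodes the 25 completers per group on which precision rests. That goes too far. Protocol 7.3.1 calls for all Week 24 assessments at early termination, the Efficacy Population needs only one post-treatment SALT score (Protocol 11.3, SAP 4.1), and SAP 8.4.1 carries the last on-treatment score forward. The patient stays in the primary analysis, and what may be lost is a score observed at 24 weeks. Planned enrollment of about 30 per arm against 25 completers also leaves about 30 - 25 = 5 per arm.

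The number of patients affected is unknown. The only related figure is in Protocol 4.4.1: three Grade 3 or 4 hematologic changes across the 4 mg, 8 mg and placebo groups of the earlier Phase 2 study. Those grades are not shown to match the Table 3 limits, so the figure is at most indicative. The reason to act is clear instructions on safety and discontinuation, not a demonstrated effect on the primary result.

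**What to change.** Reconcile the stay-in-study sentence, the monitoring sentence, Table 3 and the 21-day rule in Protocol 7.3.1 and 8.2, so that:

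- one stated threshold governs each decision (interrupt, resume, remain, discontinue);
- the direction of recovery is correct for every row, including high platelets;
- 7.3.1 and 8.2 use the same verb and the same scope for the 21-day rule;
- the text says whether interruption at a Table 3 value is mandatory or at the Investigator's discretion.

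The sponsor should also confirm that the difference between the hemoglobin cut-offs in Exclusion 13c and the Table 3 resumption levels is intended. The values and the clinical rule are for the clinical team to choose.

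The cost is amendment wording, with no added visits, tests or analyses. Because the change bears on patient safety, it probably would not count as administrative under Protocol 12.4 and would need IRB approval before sites apply it.

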8.3. Treatment Compliance

At each scheduled study visit after randomization, the Investigator or designee will interview the patient regarding treatment compliance and compare the number of dispensed versus returned study drug tablets. Patients should strive for 100% compliance with the daily dosing schedule. Retraining on treatment compliance should occur for patients with less than 80% compliance at any visit and the Sponsor should be notified.

8.4. Study Drug Materials and Management

Please consult the Pharmacy Manual for a complete description of the study drug and requirements for storage, handling, dispensing, accountability, returns and destruction.

8.4.1. Physical Description of Study Drug

Study drug will be CTP-543, a deuterated analog of ruxolitinib or an identical placebo tablet. Details regarding formulation and dosage are presented in [Table 4](#).

Table 4: Investigational Product

	Investigational Product (CTP-543 or Placebo)
Product Name:	CTP-543
Dosage Form:	Tablet
Dosage Strength of CTP-543	8 mg, 16 mg or placebo
Route of Administration	Oral
Physical Description	White, capsule-shaped tablets

8.4.2. Study Drug Packaging, Labeling, and Storage

CTP-543 active and placebo tablets will be packaged and labeled by an appropriately qualified vendor. Each patient will receive a dosing card at each 4 week study visit. Details of the packaging, labeling and dispensing instructions can be found in the Pharmacy Manual.

The label(s) for the investigational product will include sponsor name, address and telephone number, the protocol number, investigational product name, dosage form, amount of investigational product per container, lot number, unique dosing card number, storage conditions, and required caution statements and/or regulatory statements, as applicable. Additional information may be included on the label as applicable per local regulations.

Adequate supplies of study drug will be provided to each site. Study drug should be stored in the original package between 15°C to 25°C (59°F to 77°F), as stated on the product label, in a secure, temperature-monitored, locked area, under the responsibility of the Investigator or other authorized individual until dispensed to the patients.

Study drug dispensed to patients should be stored in the original package at room temperature as stated on the package label. No special handling procedures are required.

8.4.3. Study Drug Preparation and Administration

No study drug preparation is required. Patients will take the first dose of study drug in the clinic on Day 1 and will be instructed to take study drug every 12 hours. Patients should dose study drug in the clinic on all Study Visit Days after clinical laboratory blood draws are completed.

Study drug should be taken at approximately the same times each day, with water, and consistently with or without meals. Patients should be instructed to take study drug as prescribed according to the Week, Day, and Time of day designations in the dosing card. If a dose is missed, the patient should skip the missed dose and resume dosing at the next scheduled dose. The patient should not take two doses at the same time. Deviations from prescribed dosing should be discussed at each visit for assessment of compliance and retraining when necessary.

8.4.4. Study Drug Return and Disposal

The Sponsor (or designee) will review with the Investigator and relevant site personnel the process for study treatment return, disposal, and/or destruction, including responsibilities for the site versus the Sponsor (or designee). Specific requirements for destruction or return are defined in the Pharmacy Manual.

8.4.5. Study Drug Accountability

To satisfy regulatory requirements regarding drug accountability, all study drug will be reconciled in full. The Investigator or designee must maintain accurate records of the receipt of study drug, including date received, lot number, amount received, condition of the package, and the disposition of study drug.

Current dispensing records will also be maintained, including the date and amount of medication dispensed to each individual patient. Returned study drug records will be maintained and final study drug reconciliation will also be recorded for each patient.

8.5. Concomitant Medications and Procedures

All medications, including over-the-counter therapies (e.g., vitamins, herbal, and nutritional supplements), taken at the time of the Screening Visit through the Follow-Up Visit will be recorded in the patient's source documentation and documented in the eCRF.

Any concomitant medication deemed necessary for the wellbeing of the subject may be given at the discretion of the Investigator. Use of medications that are prohibited per protocol will require patient withdrawal from the study.

The following treatments are not permitted during the study:

- Medications that may affect hair regrowth or immunosuppression (such as: corticosteroids administered orally, by injection, or applied to areas of skin affected by alopecia; topical application of anthralin, squaric acid, diphenylcyclopropenone, or minoxidil);
- Treatment with systemic immunosuppressive medications including but not limited to methotrexate, cyclosporine, and azathioprine; chloroquine derivatives; Janus kinase inhibitors (ruxolitinib, tofacitinib, etc), etanercept; or biologics (adalimumab, atlizumab, canakinumab, certolizumab, fontolizumab, golimumab, infliximab, mepolizumab, rituximab, secukinumab, tocilizumab, ustekinumab);
- Use of strong CYP3A4 inhibitors (such as, but not limited to clarithromycin, conivaptan, grapefruit juice, indinavir, itraconazole, ketoconazole, lopinavir/ritonavir, mibefradil, nefazodone, neflifavir, posaconazole, saquinavir, telaprevir, telithromycin, voriconazole, or fluconazole);
- Use of strong CYP3A4 inducers (such as, but not limited to barbiturates, carbamazepine, efavirenz, glucocorticoids, modafinil, nevirapine, oxcarbazepine, phenobarbital, phenytoin, pioglitazone, rifabutin, rifampin, St. John's Wort, or troglitazone).

9. STUDY ASSESSMENTS AND PROCEDURES

The schedule of assessments and procedures is presented in

[Table 1](#) should be referenced for details regarding the collection of each assessment at each visit.

9.1. Demographic Characteristics and Medical History

Demographic characteristics (i.e., sex, ethnic origin, date of birth, and calculated body mass index) will be collected at the Screening Visit, between Day -28 and -1, and detailed on the eCRF.

The patient's alopecia areata will be classified by the Investigator into one of three categories defined for this study:

- 1) Alopecia areata: patchy type hair loss,
- 2) Alopecia totalis or universalis: complete hair loss on the scalp with or without body hair loss,
- 3) Alopecia ophiasis: band-like hair loss limited to the periphery of the scalp along the back of the hair line in the occipital region and possibly extending over each ear in temporal regions.

Key criteria that distinguish alopecia areata from other forms of hair loss may include abrupt onset of disease, a history of recurrence and spontaneous remission, response to topical or intralesional steroid treatment, and distribution of hair loss pattern. Care must be taken during the evaluation to assess for other causes of hair loss such as trichotillomania, or scarring alopecia and other forms of non-scarring alopecia. Evidence of thinning hair should be distinguished from pattern hair loss or telogen effluvium and evidence of inflammation should be investigated to rule out infection, as appropriate.

Thorough medical history, including current medications, nail and facial hair involvement, comorbidities, serious infection history and exposure risk, including HIV, as well as history or vaccination against herpes zoster will be collected at the Screening Visit, and at the Randomization Visit on Day 1.

Medical history should be thoroughly probed for potential exposure to serious infections such as HIV, history or vaccination against herpes zoster, as well as cancer risk due to the potential immunosuppressive properties of CTP-543 and known adverse events associated with JAK inhibitors.

9.2. Severity of Alopecia Tool (SALT)

The SALT score was introduced as part of investigative guidelines published by the National Alopecia Areata Foundation [[Olsen 2004](#)]. The SALT is a measure of hair absence that quantifies the amount of scalp surface without hair in a pre-specified quadrant of the scalp (right side, top, left side, back), that is further summed after applying a quadrant-specific multiplier indicative of scalp surface area contribution, to provide an overall score of total hair loss. The SALT assessment will occur via live examination of the patient during clinic visits.

SALT will be used to determine efficacy for the study. To reduce variability, one rater should perform the SALT assessment for the patient for the duration of the study. All investigators using the SALT should be trained prior to use. Please consult the associated Site Operations

Manual for additional details regarding SALT scoring and training requirements for this study. An example of the SALT assessment tool is provided in Appendix [16.1](#).

